4. STUDY OBJECTIVES AND ENDPOINTS

Part 1

Primary Objective	Primary Endpoint	
To evaluate the safety and tolerability of BIIB105 in participants with ALS or polyQ-ALS.	Incidence of AEs and SAEs in Part 1.	
Secondary Objective	Secondary Endpoints	
To assess the PK profile of BIIB105 in serum and CSF of participants with ALS or polyQ-ALS.	Serum and CSF concentrations of BIIB105 in Part 1. To evaluate the following serum PK parameters in Part 1:	
To evaluate the biomarker effect of BIIB105 in participants with ALS or polyQ-ALS.	Secondary biomarker measure: • Changes from baseline in plasma levels of NfL in Part 1	
Exploratory Objectives	Exploratory Endpoints	
To evaluate the PD effect of BIIB105 in participants with ALS or polyQ-ALS.	 Exploratory PD measure: Change from baseline in CSF levels of ATXN2 protein in Part 1. 	

Part 2

Primary Objective	Part 2 Primary Endpoint
To evaluate the long-term safety and tolerability of BIIB105 in participants with ALS or polyQ-ALS.	Incidence of AEs and SAEs in Part 2.

Integrated Part 1 and Part 2

Primary Objective	Primary Endpoint
To evaluate the long-term safety and tolerability of BIIB105 in participants with ALS or polyQ-ALS.	Incidence of AEs and SAEs during the BIIB105-treated period in Part 1 and/or Part 2.
Secondary Objective	Secondary Endpoints
To assess the long-term PK profile of BIIB105 in serum and CSF of participants with ALS or polyQ-ALS.	Serum and CSF concentrations of BIIB105 in Part 1 and Part 2. CSF trough PK concentration Serum PK concentration if available
To evaluate the long-term biomarker effect of BIIB105 in participants with ALS or polyQ-ALS, and, where relevant, to assess the impact of earlier initiation of BIIB105 (i.e., at start of Part 1) compared with delayed initiation of BIIB105 (i.e., at start of Part 2) on biomarkers.	• Changes from Part 1 baseline (Cohorts D1, D2) or Part 2 baseline (Cohorts A, B, C1, C2) in plasma levels of NfL
To evaluate the long-term effect of BIIB105 on measures of clinical function and, where relevant, to assess the impact of earlier initiation of BIIB105 (i.e., at start of Part 1) compared with delayed initiation of BIIB105 (i.e., at start of Part 2) on measures of clinical function.	Changes from Part 1 baseline (Cohorts D1, D2) or Part 2 baseline (Cohorts A, B, C1, C2) in the following assessments: • SVC • ALSFRS-R score • Muscle strength, as measured by HHD Survival analyses: • Time to death or permanent ventilation (≥ 22 hours of mechanical ventilation [invasive or noninvasive] per day for ≥ 21 consecutive days)

	 Time to death Time to death, incorporating post-study withdrawal or study completion vital status data
Exploratory Objectives	Exploratory Endpoints
To evaluate the long-term PD effect of BIIB105 in participants with ALS or polyQ-ALS, and, where relevant, to assess the impact of earlier initiation of BIIB105 (i.e., at start of Part 1) compared with delayed initiation of BIIB105 (i.e., at start of Part 2) on the PD measure.	 Exploratory PD measure: Change from Part 1 baseline (Cohorts D1, D2) or Part 2 baseline (Cohorts A, B, C1, C2) in CSF levels of ATXN2 protein.

This study collects samples that under separate optional consent may be used for future scientific and genetic research. Objectives related to this future research have not been determined.

5. STUDY DESIGN

5.1. Study Overview

5.1.1. Part 1

Part 1 is a Phase 1/2, randomized, double-blind, placebo-controlled, MAD evaluation of the safety, tolerability, and PK of BIIB105, administered IT to approximately 98 participants (76 participants with ALS and 22 participants with polyQ-ALS) at approximately 15 sites globally. Cohorts A, B, C1, and C2 will receive up to 5 doses over approximately 3 months. Cohorts D1 and D2 will receive up to 8 doses over approximately 6 months.

Approximately 98 participants are planned to be randomized in Part 1. Participants who withdraw may be replaced in a cohort at the discretion of the Sponsor. With potential replacement, approximately 108 participants could be randomized.

Adult participants with ALS will be randomized at a ratio of 3:1 (active drug:placebo) in Cohorts A, B, C1, and D1. Adult participants with polyQ-ALS will be randomized at a ratio of 3:1 in Cohort C2 and at a ratio of 2:1 in Cohort D2. Cohorts C1 and C2 can dose concurrently. Cohorts D1 and D2 can dose concurrently.

If dosing stops at one of the lower dosing cohorts, the cohort with the highest tolerated dose may be expanded to include an additional 20 participants with ALS (3:1, active drug:placebo) and an additional 18 participants with polyQ-ALS (2:1, active drug:placebo).

The first 2 participants in all cohorts, except cohort C2, will be randomized at a ratio of 1:1 (active drug:placebo) and dosed as a sentinel group. No other participants within the cohort will be dosed until the Investigators have reviewed 72 hours of safety data after dosing the first 2 participants and communicated with the Sponsor Medical Director and Global Medical Safety Physician. Based on this safety evaluation, the Sponsor will determine if the rest of the cohort can be dosed. For the remainder of participants in all cohorts, except for cohort C2, no more than 2 participants will receive their first dose of study treatment on the same day throughout the study. For cohort C2, the participants will be randomized 3:1 (active drug:placebo). Treatment will be staggered by 72 hours for the first 2 participants. The first 2 participants will be dosed as a sentinel group, and no other participant will be dosed until the Investigators have reviewed safety data after dosing the first 2 participants and communicated with the Sponsor Medical Director and Global Medical Safety Physician. This phone call will occur 72 hours after the dosing of the second participant. Based on this safety evaluation, the Sponsor will determine if the rest of the cohort can be dosed. If approved, the third and fourth participants may receive their first dose of study treatment on the same day.

For each participant, a review of all available safety and tolerability data will be performed approximately 7 days after the first dose is administered and before administration of the second dose on Day 15. This single-dose review will be performed by the site's Principal Investigator or

designee and communicated to the Sponsor Medical Director and Global Medical Safety Physician, or their appropriate designees. The Sponsor Medical Director and Safety Physician will determine if each participant can proceed with subsequent doses. The second dose cannot be administered until this review is complete.

Randomization will be performed using IRT. See Figure 1 for a schematic of the study design.

5.1.2. Part 2

Part 2 is an open-label evaluation of BIIB105 administered IT to participants with ALS and polyQ ALS who have completed Part 1 through Week 25 (Day 175 Visit for Cohorts A, B, C1, C2; Day 176 Visit for Cohorts D1, D2).

Participants will receive up to approximately 41 doses in Part 2. Two dose levels will be administered – participants from Part 1 Cohorts A, B, C1, and C2 will receive 60 mg BIIB105; participants from Part 1 Cohorts D1 and D2 will receive 120 mg BIIB105.

In Part 2, the 60 mg dose may be increased, at the Sponsor's discretion, to doses up to 120 mg. Before increasing the dose level, the SST must review safety and PK data for Cohorts D1 and D2 (Part 1) and there must be agreement that the current emerging safety, tolerability, and PK data support the dose increase. Doses in Part 2 may also be decreased at the Sponsor's discretion at any time during the study.

5.2. Study Duration for Participants

5.2.1. Study Duration for Participants in Part 1

The total Part 1 study duration for each participant in Cohorts A, B, C1, and C2 will be approximately 29 weeks:

- Screening Period of up to 4 weeks
- Treatment Period of 13 weeks
- Follow-up Period of approximately 12 weeks

Participants in Cohorts A, B, C1, and C2 will have up to 13 CVs and 9 TC during the study, which include at least 1 Screening Visit, 5 Dosing Visits of which the first dose will require an inpatient stay of 2 days, 7 Follow-up Visits, and 9 TC. All visits should be performed within the number of days from the nominal visit day, specified in Section 1. Visit days are calculated with respect to Day 1 (the date of first dose).

The total Part 1 study duration for each participant in D1 and D2 will be between approximately 29 and 41 weeks:

• Screening Period of up to 4 weeks

- Treatment Period of 25 weeks
- Follow-up Period of approximately 12 weeks (only completed if the participant does not enter Part 2 after the Treatment Period)

Participants in Cohorts D1 and D2 will have up to 19 CVs and 15 TCs which will include at least 1 Screening Visit, 8 Dosing Visits of which the first will require an inpatient stay of 2 days, up to 10 Follow-up Visits, and up to 15 TCs.

Participants in Cohorts D1 and D2 who enter Part 2 after their Treatment Period (after the Day 176 Visit) will not be required to complete the follow-up visits in Part 1 that occur after their enrollment in Part 2. Participants from Cohorts D1 and D2 who do not enter Part 2 will have two follow-up clinic visits and two TCs approximately 6 and 12 weeks after their last dosing visit.

Of note, if the Study Sponsor decides to terminate Part 1 without terminating Part 2, participants who are active in Part 1 at the time of the Sponsor's decision will have the opportunity to end Part 1 and screen and enroll into Part 2 prior to completing Week 25.

5.2.2. Study Duration for Participants in Part 2

Study duration for each participant in Part 2 will be up to approximately 172 weeks:

- Screening Period of up to 4 weeks (for participants from Cohorts D1 and D2, Screening Period begins with Day 169 Visit of Part 1)
- Treatment Period of up to approximately 156 weeks: either 104 weeks, OR until the last participant enrolled has had the opportunity for their Part 2 Day 365 visit (Week 52), whichever occurs later
- Follow-up Period of approximately 12 weeks

Participants will have up to approximately 44 CVs and 43 TCs during Part 2 of the study, which will include at least 1 Screening Visit, up to approximately 41 Dosing Visits, 2 Follow-Up Visits, and up to 43 TCs.

The end of study date for a participant may be the last study visit, last follow-up TC, or last protocol-specified assessment, or if the participant has ongoing AEs that are being followed up, the date may be the date of AE resolution.

After a participant's end of study date, follow-up on vital status and date of death (if deceased) will be performed for participants who provide optional consent for data collection after study completion.

5.3. Dosing

5.3.1. Dose Escalation (Part 1)

For each dose escalation, safety (AEs/SAEs, vital signs, ECGs, and laboratory parameters) and available PK data will be reviewed. The proposed dose escalation is illustrated in Figure 1 and the proposed dosing groups are as follows:

Participants with ALS:

Cohort A: BIIB105 5 mg (6 participants) or placebo (2 participants)

Cohort B: BIIB105 20 mg (6 participants) or placebo (2 participants)

Cohort C1: BIIB105 60 mg (9 participants) or placebo (3 participants)

Cohort D1: BIIB105 120 mg (approximately 36 participants) or placebo (approximately 12 participants)

Participants with polyQ-ALS:

Cohort C2: BIIB105 60 mg (3 participants) or placebo (1 participant)

Cohort D2: BIIB105 120 mg (approximately 12 participants) or placebo (approximately 6 participants)

See Section 3.1.2 for details regarding the rationale for the starting dose and dose escalation.

After a cohort (Cohorts A, B, C1, and C2) is fully randomized and at least 36 days have elapsed since the randomization and dosing of the eighth participant, a Sponsor SST will hold a dose escalation meeting to review all available blinded safety data from all randomized participants. There must be a minimum of 6 evaluable participants for the dose escalation meeting to occur. In Cohort C2, all 4 participants must be evaluable for the dose escalation meeting to occur. Evaluable participants are defined as those who have completed 3 dosing visits and the Day 36 CV. This CV occurs 1 week after the Day 29 dose, the dose that is projected to result in the targeted steady-state exposures for the cohort. Dosing of Cohort D1 is dependent on the SST approving the safety of Cohort C1, and dosing of Cohort D2 is dependent on an SST approving the safety of Cohort C2.

For Cohort D1, the safety review will occur after the cohort is fully randomized, and at least 92 days have elapsed since the randomization and dosing of the 36th participant. The SST will review all available blinded safety data from all randomized participants in the cohort, which must include a minimum of 33 evaluable participants (those who completed all of the first 5 dosing visits as well as the Day 92 clinic visit). This review will be for a final safety review for Cohort D1. Should Part 1 be terminated early (per Section 5.2.1 and Section 13.4) prior to reaching randomization of the entire D1 cohort or minimal evaluable criteria as defined, a final

safety SST will be held for Cohort D1 with all available safety data at the time of Part 1 termination.

For Cohort D2, the safety review will occur after the cohort is fully randomized, and at least 92 days after the randomization of the 15th participant. The SST will review all available blinded safety data from all randomized participants in the cohort, which must include a minimum of 12 evaluable participants (those who completed all of the first 5 dosing visits as well as the Day 92 clinic visit). This review will be for a final safety review for Cohort D2. Should Part 1 be terminated early (per Section 5.2.1 and Section 13.4) prior to reaching randomization of the entire D2 cohort or minimal evaluable criteria as defined, a final safety SST will be held for Cohort D2 with all available safety data at the time of Part 1 termination.

Cohorts D1 and D2 can be reviewed concurrently or in separate SSTs, depending on when the cohorts have reached the minimum evaluable patients.

Principal Investigators from sites where participants were dosed will be included in the blinded safety data review. Review of blinded safety data may be followed by review of unblinded safety data of the current and preceding cohorts by the SST. Details of the unblinded review as well as the personnel to be unblinded to support dose escalation will be clearly defined in the Dose Escalation Plan and Unblinding Plan for this study.

In addition to the review of all safety data, there will be a review of available PK data collected through the third dose prior to dosing of the next dose cohort for Cohorts A, B, C1, and C2. For Cohort D1, there will be a review of all available PK data for a minimum of 33 evaluable participants. For Cohort D2, there will be a review of all available PK data for a minimum of 12 evaluable participants. Should Part 1 be terminated early (per Section 5.2.1 and Section 13.4) prior to reaching randomization of the entire D1 and/or D2 cohorts or minimal evaluable criteria as defined, a final safety SST will be held for Cohort D1 and/or D2 with all available PK data at the time of Part 1 termination.

Before escalating to the next higher dose level, there must be agreement that the current emerging safety, tolerability, and PK data support dose escalation. The appropriate quality control checks on the reviewed data and the conclusions of the SST will be documented in writing before allowing study progression.

Safety monitoring will continue after dose escalation, in accordance with the visit schedule, which encompasses approximately 12 additional weeks of follow-up.

5.3.2. Dosing (Part 2)

Dosing in Part 2 will begin at the Sponsor's discretion. Prior to start of dosing, the SST must review safety and PK data from Cohorts C1 and C2 (Part 1) and there must be agreement that the current emerging safety, tolerability, and PK data support the start of dosing in Part 2.

Participants who were assigned to Cohorts A, B, C1, and C2 and who have completed Week 25 (Day 175) Visit in Part 1 will receive BIIB105 at 60 mg in Part 2. Participants who were

assigned to Cohorts D1 and D2 and who have completed Week 25 (Day 176) Visit in Part 1 will receive BIIB105 at 120 mg in Part 2. The 60 mg dose may be increased, at the Sponsor's discretion, to doses up to 120 mg. Before increasing the dose level, the SST must review safety and PK data for Cohorts D1 and D2 (Part 1) as described in the Dose Escalation Plan and there must be agreement that the current emerging safety, tolerability, and PK data support the dose increase. Doses in Part 2 may also be decreased at the Sponsor's discretion at any time during the study.

Participants who were assigned to Cohorts A, B, C1, and C2 will have a ≥16-week washout period between the time of their last dose of study treatment in Part 1 and their first dose in Part 2. Therefore, they will have a 4-week unblinded Loading Dose Period, during which they will receive 3 doses of BIIB105 administered every 2 weeks (on Days 1, 15, and 29).

Participants who were assigned to Cohorts D1 and D2 will not have had a washout period between their last dose of study treatment in Part 1 and their first dose in Part 2. Therefore, they will have a 4-week blinded Loading Dose Period, to protect the blind in Part 1. During this blinded Loading Dose Period, participants who received BIIB105 during Part 1 will receive two doses of BIIB105, on Days 1 and 29, and placebo on Day 15. Participants who received placebo in Part 1 will receive three doses of BIIB105 administered every 2 weeks (on Days 1, 15, and 29). Participants from Cohorts D1 and D2 must not receive their first dose in Part 2 sooner than 4 weeks after their last dose in Part 1.

For all participants, the Loading Dose Period will be followed by an unblinded Maintenance Dose Period, where participants will receive maintenance doses of BIIB105 administered once every 4 weeks (up to approximately Week 156: either to Week 104, OR until the last participant enrolled has had the opportunity for their Part 2 Day 365 visit [Week 52], whichever occurs later). After the Maintenance Dose Period, participants will have an approximately 12-week follow-up period.

The SST will review safety and PK data from the extension cohorts at regular intervals.

5.4. Study and Cohort Stopping Rules

5.4.1. Cohort Suspension

If 1 participant experiences either an SAE or a medically unacceptable AE (as defined by the Investigator or the Sponsor), the Sponsor Medical Director and Global Medical Safety Physician will review relevant safety information and obtain more information from the Investigator, if necessary. If the AE is assessed as unrelated to study treatment by both the Investigator and the Sponsor (e.g., is a known sign or symptom of ALS or is a known effect of the LP procedure), dose suspension is not necessary.

If the SAE or medically unacceptable AE (as determined by the Investigator or the Sponsor) is assessed as related to study treatment by the Investigator or the Sponsor, then dosing at and above the dose level at which the event occurred will be suspended until the event has been fully evaluated by the SST. Depending on the nature, severity, suspected on- or off-target toxicity,

outcome, and frequency of the event, a decision (documented with supporting rationale) will be made to proceed with one of the following:

- Request additional safety data.
- Continue dosing the remaining participants within the cohort.
- Randomize additional participants to the current cohort.
- Enroll additional participants to previous (lower dose) cohort.
- Proceed with the planned dose escalation in the next cohort.
- Dose a cohort with an intermediate lower dose.
- Stop the study.

The review will also include all available preliminary PK data from the current and preceding cohort(s).

If the study is suspended, dosing of the cohort cannot resume until both of the following have occurred:

- The Sponsor SST has completed the safety evaluation and the Investigator has received written approval from the Sponsor to resume dosing, and
- Where applicable, a rationale for the continuation of the study, including an amended protocol if required, is submitted to the relevant regulatory agency(ies) as a substantial amendment and subsequently approved before dosing can resume.

Following the SST review of safety and PK data for Cohort D1 (Part 1), if there is agreement that the current emerging safety, tolerability, and PK data support continued dosing at 120 mg, the abovementioned dose suspension rules will no longer apply. The Sponsor may still determine that a dose suspension is required at any time due to emerging safety data.

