5.4.2. Dose Termination

After evaluation of safety, tolerability, and PK data by the SST, Investigator, and if required, any ad hoc members, further dosing at the current level and dose escalation will be terminated if any of the following is observed:

- Three similar SAEs (unless related to disease progression or unrelated to BIIIB105 upon medical review) are reported for participants receiving active study treatment within the same cohort.
- Four or more similar AEs are reported for participants receiving active study treatment (unless related to disease progression or unrelated to BIIIB105 upon

CONFIDENTIAL

The information contained herein may not be used, disclosed, or published without the written consent of Biogen MA Inc.

medical review) that are either not tolerable (as reported by the participant) or deemed a medically unacceptable risk by the SST.

• Sponsor requests that dosing be terminated.

Following the SST review of safety and PK data for Cohort D1 (Part 1), if there is agreement that the current emerging safety, tolerability, and PK data support continued dosing at 120 mg, the abovementioned dose termination rules will no longer apply. The Sponsor may still determine that a dose termination is required at any time due to emerging safety data.

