13.5. Sample Size Considerations

Part 1:

The sample size of this first-in-human clinical study was selected with the goal of balancing between safety and tolerability considerations in dose escalation and obtaining sufficient initial information related to the safety and biological activities of BIIB105. Sample sizes of 6 participants receiving active treatment in lower dose Cohorts A and B will allow an greater probability to observe at least 1 occurrence of an AE with event rates of or greater. The sample size of 9, 36, and 12 participants exposed to active doses in Cohorts C1, D1, and D2, respectively, allow an or greater probability to observe at least 1 occurrence of an AE with event rates of one of greater, respectively.

Cohort C2 will expose 3 participants with polyQ-ALS to active treatment as part of additional dose escalation step specifically for participants with intermediate-repeat CAG expansions in *ATXN2* gene as they may be more sensitive to the effects of BIIB105. The sample size of 3 was selected solely as precaution step before exposing participants with polyQ-ALS to 120 mg dose of BIIB105 in Cohort D2.

The sample size of Cohort D1 provides approximately % power to detect a % difference in the ratio to baseline in plasma NfL, in the BIIB105 versus placebo group, based on Cohort D1 120 mg data (N on BIIB105 = 36) vs pooled placebo data across Cohorts A through D1 (N = 19), with 2-sided % significance level, assuming % SD in both groups.

Part 2:

The sample size of Part 2 is based on the sample size of Part 1. Up to approximately 98 participants will be dosed in Part 2.

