15.2. Study Committees

15.2.1. Safety Surveillance Team

The Sponsor's SST will serve as the study committee. The composition of the SST will follow Sponsor standard operating procedures. The SST, as described in Section 5.3, is responsible for reviewing the safety and PK data prior to dose escalation and at regular intervals in Part 2 and determining whether SAEs and clinically significant AEs result in cohort or study suspension.

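### Sections 5.4.1 and 5.4.2 let the Cohort D1 review end the stopping rules for polyQ-ALS participants on 120 mg before the Cohort D2 review, and Section 7.1 omits D2 from the 60-to-120 mg gate

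*Protocol*

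**What the plan says.** **Suspension.** Under Protocol Section 5.4.1, after an SAE or medically unacceptable AE judged related to treatment, "dosing at and above the dose level at which the event occurred will be suspended" until the SST has evaluated it. The last paragraph of that section ends the rule: it lapses if, after the SST review of Cohort D1, there is agreement that the data "support continued dosing at 120 mg, the abovementioned dose suspension rules will no longer apply".

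**Termination.** Section 5.4.2 lists criteria that end dosing at a level after evaluation by the SST and Investigator. Three similar SAEs count when they "are reported for participants receiving active study treatment within the same cohort"; a second criterion, four or more similar AEs, is not tied to a cohort. The section closes on the same condition: if the data "support continued dosing at 120 mg, the abovementioned dose termination rules will no longer apply".

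**Reviews.** Section 5.3.1 gives D1 (ALS) and D2 (polyQ-ALS) a final safety review each, and adds: "Cohorts D1 and D2 can be reviewed concurrently or in separate SSTs, depending on when the cohorts have reached the minimum evaluable patients".

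**PolyQ-ALS as a separate line.** Section 5.3.1 states that "dosing of Cohort D2 is dependent on an SST approving the safety of Cohort C2", while D1 depends on C1. Section 13.5 explains that polyQ participants may respond more strongly to the drug, and says of Cohort C2: "The sample size of 3 was selected solely as precaution step before exposing participants with polyQ-ALS to 120 mg dose".

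**Part 2 increase from 60 to 120 mg.** Section 7.1 requires SST review of Cohort D1. Sections 5.1.2 and 5.3.2, and Section 2.2 of the Part 2 and integrated SAP, require review of D1 and D2.

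**The concern.** The protocol treats polyQ-ALS separately at each earlier safety step: its own 60 mg cohort, its own clearance to start 120 mg, and its own final review at 120 mg. The last paragraphs of 5.4.1 and 5.4.2 break that pattern. They use the ALS cohort's review to end the rules for everyone and require no minimum of D2 data.

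At stake is a default. While 5.4.1 applies, one related SAE in D2 stops dosing first and is evaluated afterwards. Once it has lapsed, dosing goes on unless someone decides to stop it. The three-SAE criterion in 5.4.2 is counted cohort by cohort, yet another cohort's review can remove it for D2.

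Section 7.1 raises a related problem. The Part 2 60 mg group includes Cohort C2, so a site working from the Regimen section alone would see a gate that needs no polyQ data at 120 mg.

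**Working it through.** The plan states no figure to reproduce. The check sets the sections side by side.

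**1. The two reviews (Sections 5.1.1 and 5.3.1).**

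| | D1 (ALS) | D2 (polyQ-ALS) |
|---|---|---|
| Planned active + placebo | 36 + 12 = 48 | 12 + 6 = 18 |
| Dosing starts after SST clears | C1 | C2 |
| Earliest review | fully randomised, 92 days after 36th participant | fully randomised, 92 days after 15th participant |
| Minimum evaluable | 33 | 12 |

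The start gates, recruitment pools and milestones all differ, and the two cohorts may dose concurrently.

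**2. Possible orders.**
- D2 reviewed before D1: no gap.
- Both reviewed together: no gap.
- D1 reviewed first with agreement: the rules end for D2 while its review is pending. D2 may then have fewer than 12 evaluable participants, possibly none.

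The protocol permits all three.

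**3. Who could be in the gap.** The 12 active D2 participants are the core group. The 6 D2 placebo participants join it only if they start 120 mg in Part 2 before the D2 review: 12 + 6 = 18. Cohort C2 (3 + 1 = 4) receives 60 mg in Part 2. Under 5.1.2 and 5.3.2 those four should not reach 120 mg until D2 data have been reviewed; under 7.1 read alone they could. The total of 18 + 4 = 22 matches the polyQ count in Section 5.1.1.

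**4. What lapses.** The two rules work differently. Section 5.4.1 pauses dosing first and evaluates second. Section 5.4.2 acts only after SST and Investigator evaluation and allows medical-review exceptions, so it sets criteria for a decision and is not an automatic stop.

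**5. What stays.**
- Section 5.1.1: sentinel dosing of the first two participants with a 72-hour review, and a review about 7 days after each participant's first dose, without which the second dose cannot be given.
- Section 5.3.1: the D2 review itself, held on available data if Part 1 ends early.
- Section 5.3.2: regular SST review in Part 2.
- Sections 5.4.1 and 5.4.2: Sponsor discretion to suspend or terminate.
- Section 15.2.1: the SST's responsibility for "determining whether SAEs and clinically significant AEs result in cohort or study suspension".

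The Section 5.1.1 protections act around the first dose. They do not replace the pause for later loading and maintenance doses.

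**6. Why no probability is given.** The chance of an SAE in the gap would need the related-SAE rate, the length of the gap and the number exposed. The documents give neither of the first two, and the third can range up to 18.

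**7. The 60-to-120 mg gate.** Section 7.1 names D1. Sections 5.1.2 and 5.3.2 and Section 2.2 of the Part 2 SAP name D1 and D2. Meeting 5.1.2 also meets 7.1, but meeting 7.1 does not meet 5.1.2. The texts therefore disagree on what must happen before escalation.

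**The case against.** The strongest reply is that tying the lift to D1 was deliberate. The Version 3.0 amendment rationale says benefit/risk at the top dose will by then have been assessed, and that participants will be moving into the extension with no further escalation. The Version 5 summary aligns the termination rules with this and notes that SST review continues. The precaution attached to polyQ sensitivity is Cohort C2, and that gate is intact. The SST agreement rests on current data, so the team can look at whatever D2 data exist and withhold agreement. Review conduct is partly deferred to a Dose Escalation Plan that is not among the documents and might fix the order.

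Most of this stands as mitigation. It does not answer the point, because the stated reasons do not address polyQ participants whose 120 mg review is still pending, and the text leaves use of D2 data optional.

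On 7.1, the reply is that this is a missed conforming edit: the Version 5 summary records the D2 requirement as added to Section 5.1.2. That is probably how it arose, but the sentence states an operative safety gate.

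A reader might infer that polyQ participants are left without safety oversight. They are not, given the protections listed in the working. A reader might also infer from the Part 2 SAP, which reports that 60 mg was raised to 120 mg after an SST review on 13 December 2023, that the gap occurred or that D2 was skipped. The SAP does not say what that review covered or in what order D1 and D2 were reviewed.

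**Conclusion.** Both parts hold for the protocol as written.

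- **Stopping rules: a cheap improvement.** If D1 is reviewed first with agreement, the pause-then-evaluate rule of 5.4.1 and the criteria of 5.4.2 can end for polyQ participants on 120 mg before the D2 review. The reach is up to 12 active D2 participants in Part 1, or 18 with D2 placebo participants who have started 120 mg in Part 2. This rests on the planned cohort sizes and on no document outside those supplied fixing the review order. The gap is nil if the reviews coincide or D2 comes first.
- **Section 7.1: wrong as written.** It states a weaker gate than 5.1.2, 5.3.2 and the Part 2 SAP.

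Whether the gap ever affected anyone cannot be determined. The Part 2 SAP also reports that the Sponsor later stopped the study early for lack of effect, so the point concerns the design and not its realised consequences.

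**What to change.** 1. Add to the last paragraph of 5.4.1 and of 5.4.2: *For participants with polyQ-ALS receiving 120 mg, these rules remain in force until the SST has reviewed Cohort D2 as described in Section 5.3.1 and there is agreement that the data support continuing 120 mg in polyQ-ALS. After the Cohort D1 review, only events in participants with polyQ-ALS count toward these rules, and a resulting suspension or termination applies to participants with polyQ-ALS unless the SST extends it.*
2. In 7.1, replace *Cohort D1 (Part 1)* with *Cohorts D1 and D2 (Part 1)*.

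The agreement condition is needed so that an unfavourable or inconclusive D2 review does not end the rules. Limiting the sentence to 120 mg leaves C2 participants on 60 mg out of it. Counting only polyQ events settles how the four-AE criterion works after the D1 review. Confining the consequence to polyQ-ALS stops a D2 event from pausing D1 through the dose-level wording of 5.4.1.

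The cost is protocol wording and a possible dosing pause for polyQ participants between the two reviews. No new review is needed, since 5.3.1 already schedules one. No SAP change is needed, since the Part 2 SAP already names both cohorts.
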